# Dosing

# Omega-3 Fatty Acids

Study subjects may be randomized to receive 3000mg (6 500mg capsules) of omega-3 fatty acids or placebo for the duration of the study. Omega-3 fatty acid capsules are in the form of Nordic Naturals brand, ProOmega Junior, which contains 325mg EPA and 225mg DHA per two capsules. Nordic Naturals will provide the omega-3 fatty acid placebo in addition to the active capsules.

Nordic Naturals brand is commonly used by clinic patients under our care and has been used in adult studies of bipolar disorder at Massachusetts General Hospital (PI: [name]). We chose this product for its palatability (very little fishy taste or odor, which will facilitate the blinding process), its freedom from toxins including mercury, and the size of capsule which is easy for children to swallow. As omega-3 fatty acids are difficult to obtain and must be extracted from fish, a high quality, reliable product which filters toxins and mercury is critical for use in children. Omega-3 fatty acids can also expire and decrease in potency, arguing further for a well-regarded and tested product.

The rationale for the omega-3 dosing is based on the few dosing studies in adults which suggest that lower doses (1g) are more effective that higher doses (4g) for depression in adults, plus the result of our preliminary study which found no greater efficacy beyond 2000mg. The daily dose per participant of 3000mg of omega-3 fatty acids includes 975mg EPA, which is close to the potentially helpful 1000mg (or 1g) suggested for this population.

## Inositol

Subjects weighing 25kg or more may be randomized to receive 2000mg (4 500mg capsules) of inositol, which is 80mg per kg for a 25kg child. Children weighing less than 25kg will be dosed at 80mg per kg rounded down to the nearest 500 mg capsule. Inositol will be obtained from Jarrow Formulas, a supplier of nutritional supplements, in capsules containing 500mg of inositol per capsule. The Massachusetts General Hospital Research Pharmacy will provide the inositol placebo pill.

Jarrow Formulas brand was chosen for the inositol based on clinical experience by the PI using various brands in clinic patients. This brand is easy to obtain and offers inositol powder, sold in bulk. The MGH Pharmacy will encapsulate the powder and provide a matched placebo. Inositol is a simple sugar substance and is easy to manufacture and obtain. There is little difference among the brands, although only some of the companies encapsulate the inositol powder.

There are no dosing studies for inositol, but the only study in children (a negative study for ADHD) found 200mg per kg to be safe and tolerable. 2000mg is 80mg per kg for a 25kg child. Weight corrected dosing will occur in the case of a child weighing below 25kg.

Double-blind omega-3 fatty acid and double-blind inositol treatment will commence on the same day. Both omega-3 fatty acid and inositol may be taken QD or BID, per clinician judgment.

Subjects who have difficulty swallowing the inositol/placebo capsules can have his/her parent(s)/guardian(s) open the capsules and put the contents into soft food (such as ice cream or apple sauce) until the child is fully trained in swallowing pills. As inositol is a natural supplement found in everyday foods, this will not present an increased risk to subject safety, nor does it change the efficacy of the study medication. Since the inositol and dextrose (the contents of a placebo pill) are both similar in appearance, administering the medication in this fashion will not break the blind. The omega-3 fatty acid capsules (and matched placebo) are smaller and more easily swallowed; however, because opening the omega-3 fatty acid capsules will likely not allow subjects to receive the entire dose and risks breaking the blind, subjects who are unable to swallow the omega-3 fatty acid/placebo capsules will be removed from the study.

Our research pharmacy is expert in the creation of blinded randomization lists, and

handling and packaging of medications for blinded trials utilizing encapsulation processes to ensure blindness by the clinicians and the subjects, who will not know which subjects are receiving omega-3 fatty acids, which are receiving inositol and which are receiving both treatments. The supplements will be stored in the research pharmacy and delivered the Pediatric Psychopharmacology Unit where it will be dispensed by a clinician. Subjects are instructed to return unused capsules. Pill counts will be reviewed each visit to ensure compliance.

# **Concomitant Medications**

A detailed past and present treatment history will be taken as part of initial evaluation. Patients who are partially responding to current psychotropic medication yet continue to have symptoms of mania and depression will be permitted to continue on their current regimen, provided the patient's regimen remains the same throughout the study. Patients treated with these medications must be on a stable dose for at least two weeks prior to study entry. No new medications (except for the use of the benzodiazepine lorazepam listed below) or alterations to the current regimen may be initiated throughout the duration of study participation.

Only patients with a poor response to their current medication treatment will be advised to consider a taper off their medications for entry into the study. Our experience with clinical trials in this population indicates that this procedure is feasible and clinically indicated in cases in which subjects are not doing well on current treatment. No patient will be tapered from medication that is useful to him or her. If at Screening a participant is taking medication for a comorbid condition, the clinician will evaluate, using a CGI scale for the targeted condition, whether or not this condition is of moderate or greater severity. If the condition is found to be of moderate or greater severity, we will interpret this as a lack of efficacy for this Concomitant Medication, and will advise the subject to taper off the medication for entry into this study. In dozens of clinical trials in children with bipolar disorder we have used this same procedure successfully.

The use of the benzodiazepine lorazepam is permitted during the study. Patients may not exceed a dosage of 2mg lorazepam per day and lorazepam is permitted for a maximum of 3 days during the study. Any greater need for lorazepam will be considered evidence of poor treatment response and grounds for drop from the study.

Additionally, participants who are on a stable dose of ADHD medications may continue on that dose throughout the study. However, no new medications for ADHD or alterations to the current ADHD regimen may be started throughout the duration of participation in the study, per clinician judgment.

Non-pharmacological treatments such as individual, family or group therapy will be allowed if they were in place before the patient joined the study. The patient's therapy regimen must remain the same throughout the study. No new non-pharmacological treatments may be initiated after study participation has begun.

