# Washout Period

Medication washout is recommended by our clinicians to families and current providers – this is done according to a case-by-case assessment, considering the duration on drug, the dose, and the adverse effects associated with the treatment, and effects of stopping that medication/treatment. Only subjects not responding to current treatment will be tapered from medication. No subject on a useful treatment will be tapered from medication for entry into this study. The referring or study clinician will monitor medication tapers in agreement with the research subject and his/her legal guardians. Our office does not take over care for the patient, but remains available during this time period. The washout schedule will be discussed with the subject's family as well as the current provider.

Typically a 7-day washout period is recommended for antidepressant medications and atomoxetine (with the exception of Prozac requiring 14 days). Mood stabilizers/atypical antipsychotics are generally washed out over the course of 7 days, while stimulants are discontinued in 2 or 3 days.

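### The Screening rule infers lack of efficacy from current CGI severity alone, so it can prompt advice to taper a partly effective drug for a comorbid condition

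*Combined protocol and SAP*

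**What the plan says.** All references are to the combined protocol and SAP.

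**The rule.** Section 7, Concomitant Medications, states: "If at Screening a participant is taking medication for a comorbid condition, the clinician will evaluate, using a CGI scale for the targeted condition". If the condition is "found to be of moderate or greater severity, we will interpret this as a lack of efficacy for this Concomitant Medication", the child is advised to taper the drug in order to enter the study.

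**Related statements in the same section.**
- Directly before the rule: "No patient will be tapered from medication that is useful to him or her".
- On partial response: "Patients who are partially responding to current psychotropic medication yet continue to have symptoms of mania and depression will be permitted to continue".
- On ADHD drugs: "participants who are on a stable dose of ADHD medications may continue on that dose throughout the study".
- On what the clinician knows: "A detailed past and present treatment history will be taken as part of initial evaluation".

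**Washout Period.** The promise is repeated: "No subject on a useful treatment will be tapered from medication for entry into this study". Of the washout recommendation, the section says "this is done according to a case-by-case assessment". The assessment weighs time on the drug, dose, adverse effects and the consequences of stopping, and guardians must agree to the taper.

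**Eligibility.** Inclusion item 8 (section 6) admits ADHD and ODD up to moderate impairment, provided it is less than the impairment from the bipolar disorder. Anxiety is admitted only at minimal impairment. Conduct disorder is excluded.

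**The scale.** Section 8 describes two CGI scores, each from 1 to 7: severity, which is current state, and improvement, which is change. The Screening rule uses severity and does not mention improvement.

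**The concern.** Efficacy is about change: how the child is on the drug compared with how the child was, or would be, without it. The Screening rule looks only at the state on drug. It cannot separate a drug that has done nothing from one that has moved a child from severe to moderate. Both are classed as lacking efficacy, and both lead to advice to stop.

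The plan recognizes the distinction elsewhere, since partial responders with remaining mood symptoms may stay on their regimen. It also accepts moderate ADHD and ODD as compatible with entry. The rule can therefore prompt a family to consider stopping a drug that helps, for the sake of a trial the child could have entered while taking it. The children are 5 to 12 years old, and once in the study their regimen is fixed apart from limited lorazepam. What is at stake is the child's care and the consistency of the plan. The treatment comparison is not at stake.

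**Working it through.** The plan gives no figure to reproduce here, so this is a check of logic and consistency with two small counts.

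**1. Does the rule measure response?** Let *s* be CGI severity before the drug and *m* the severity on it. The rule fires when *m* is at least moderate. Response is *s* − *m*, and *s* does not appear in the rule. As an illustration, assume moderate is 4; the plan anchors only 1 and 7.
- From 6 to 4: improvement 6 − 4 = 2 points, and the rule says no efficacy.
- From 5 to 4: improvement 5 − 4 = 1 point, and the rule says no efficacy.
- From 4 to 4: improvement 0, and the rule says no efficacy.

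The result does not depend on choosing 4. If moderate is any value from 2 to 6, a child who falls from a higher score to that value has improved and still triggers the rule.

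**2. Which children are caught although item 8 can admit them?** The four comorbid conditions named in item 8, taken at moderate severity on drug:

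| Condition | Item 8 at moderate | Screening rule |
|---|---|---|
| ADHD | can be admitted | taper advised, unless the stable-dose sentence exempts it |
| ODD | can be admitted | taper advised |
| Anxiety | not admitted (minimal only) | outside the overlap |
| Conduct disorder | excluded | outside the overlap |

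The overlap is 2 conditions, or 2 − 1 = 1 (ODD) if the ADHD sentence is an exemption. Conditions that item 8 does not name are outside this count.

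**3. Is the ADHD sentence an exemption?** The plan does not say. The sentence carries no severity limit, which favours an exemption. Against that, Washout Period gives washout times for stimulants (2 or 3 days) and atomoxetine (7 days), so some tapering of such drugs is foreseen. For a child with moderate ADHD on a stable dose, the text supports two different answers.

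**4. Do the safeguards supply another test of response?** Both sections promise that useful drugs are not tapered, but neither defines useful. Among the factors in the washout assessment, none is a criterion for response. For a comorbidity drug, the only stated efficacy criterion is current severity. A partly effective drug is thus useful under the promise and lacking in efficacy under the rule.

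**5. Is the rating in the schedule?** Table 1 has 14 visit columns (99, then 0 to 12). The CGI row is marked in 13 of them (0 to 12), leaving 14 − 13 = 1 unmarked, the screening visit. The Screening Visit list and the CGI entry in section 8 omit it as well. This is an omission from the schedule, because Concomitant Medications itself calls for the rating.

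**The case against.** The best reply is that the plan should be read as a whole. The ban on tapering useful drugs comes immediately before the CGI rule and is repeated under Washout Period. Subject Enrollment and Design also confine tapering to children who are not responding. The rule produces advice only; the decision is made case by case and with the guardians. On this view a moderate rating opens a discussion and cannot by itself take a child off a helpful drug. **This stands as a limit on the harm.** It does not repair the rule, which fixes both the interpretation and the advice, so the family hears that the drug lacks efficacy when that may be untrue.

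A second reply is that the partial-responder sentence refers to psychotropic medication in general, and every eligible child has manic symptoms (YMRS of at least 20). It might therefore cover a partly effective ODD drug. That is a possible reading. If it is right, the plan tells the clinician both to continue that drug and to advise stopping it, which is a further reason to settle the text.

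A third reply is that the overlap is narrow. It may be ODD only, and it equates CGI severity with item 8 impairment, which are related but different ratings. **This stands**, and the conclusion is stated with that assumption.

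Two stronger readings are tempting, and the documents do not support them.
- A reader might infer that tapering before Week 0 biases the within-arm changes tested under Hypothesis 1. The plan gives neither the share of children tapered nor any effect of stopping on YMRS or CDRS, so neither size nor direction can be derived.
- A reader might infer that the Screening rating could not be checked later because Table 1 omits it. Audio Recordings says rating scales done at visits are recorded for quality control, so an empty cell does not show that the rating would be lost.

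**Conclusion.** The concern holds as a defect in the taper criterion. Current severity on drug cannot establish non-response, and the rule treats it as if it did. It can label a partly effective drug as ineffective and prompt taper advice in a child with moderate ODD, or moderate ADHD if the stable-dose sentence is not an exemption, whom item 8 can admit on that drug. This is inconsistent with the plan's own undertaking that useful drugs are not tapered.

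The reach is two of the four comorbid conditions named in item 8, or one with the ADHD exemption. It rests on the assumption that moderate on the CGI corresponds to moderate impairment in item 8, and that the impairment is milder than the bipolar impairment. The number of children affected cannot be derived. No effect on power, sample size or between-arm tests is claimed. The change is worth making for the children's care and for consistency; the trial's inference does not depend on it.

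**What to change.** 1. **Replace the severity-only test** in Concomitant Medications. Suggested wording: *A taper will be advised only if the comorbid condition is moderate or worse on CGI-Severity and the clinician judges, from the treatment history, that the drug has given no meaningful benefit.* The decision stays with clinician and family, as now.
2. **State that the stable-dose ADHD sentence governs ADHD drugs**, so that a child with moderate ADHD on a stable dose gets one answer.
3. **Housekeeping:** for children on a drug for a comorbid condition, mark the CGI-Severity rating at visit 99 in Table 1, and add it to the Screening Visit list and the CGI entry in section 8.

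The cost is the rewording of one rule, one clarifying sentence and a schedule entry for a rating the plan already requires. No visit is added. There are two drawbacks. The benefit judgement will rest partly on recall, because Source of Subjects rules out the use of other medical records. Some children may also stay on stable co-medication who would otherwise have been advised to taper, which the plan already permits.

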# Washout Period

Medication washout is recommended by our clinicians to families and current providers – this is done according to a case-by-case assessment, considering the duration on drug, the dose, and the adverse effects associated with the treatment, and effects of stopping that medication/treatment. Only subjects not responding to current treatment will be tapered from medication. No subject on a useful treatment will be tapered from medication for entry into this study. The referring or study clinician will monitor medication tapers in agreement with the research subject and his/her legal guardians. Our office does not take over care for the patient, but remains available during this time period. The washout schedule will be discussed with the subject's family as well as the current provider.

Typically a 7-day washout period is recommended for antidepressant medications and atomoxetine (with the exception of Prozac requiring 14 days). Mood stabilizers/atypical antipsychotics are generally washed out over the course of 7 days, while stimulants are discontinued in 2 or 3 days.

# Screening Visit

Before any participant can start the study, the study clinician will discuss the details of the study with the participant and his/her parent/guardian. Before starting the screening process, the study clinician will obtain informed consent from the parent or guardian and assent from the child subject. Assent will be obtained, in writing, from each child age 7-12 years who, in the opinion of the Investigator, is capable of providing assent based on their age, maturity, and psychological state. When assent is not obtained, the Investigator will document his/her rationale in the research records.

After the consent/assent form is signed, we will do the following:

- Review medical and health questions with the participant and their parents/guardians. (For example, "Does your child have a history of any medical conditions such as diabetes or hypertension?")
- Conduct a brief demographic interview. This interview will be used to estimate socioeconomic status, as well as collect information about any educational accommodations, and past head injuries and trauma.
- Obtain psychiatric history and administer YMRS, the CDRS, the HAM-D, the C-SSRS, and the K-SADS-E mania and depression modules to determine that subject meets the diagnostic criteria of a current DSM-IV bipolar spectrum disorder (mixed, manic, or hypomanic) and has an YMRS score of ≥ 20 and < 40.

All exclusionary and inclusionary criteria will be reviewed. Appropriate patients will undergo:

- An assessment battery (CBCL, SAICA, FES)
- Cognitive evaluation [IQ and cognitive function (subtests of WISC-IV, WPPSI-III, or KBIT-2)]

- Select WPPSI-III subtests will be used in the place of the WISC-IV processing speed subtest for children younger than 6 years.
- The KBIT-2 will be used in the place of the WISC-IV to assess IQ in children younger than 6 years.
- Physical exam
- Tanner staging exam (clinician-administered to parent or subject, clinician exam with subject, or the option to refuse)
- Vital Signs (blood pressure, pulse, height, weight, temperature)

The above may take place over two visits over the course of three weeks, if necessary. All are to be completed prior to the Baseline Visit. Any subjects requiring medication washout must be tapered off this medication prior to Baseline Visit as indicated in the washout section. Patients who do not meet all the criteria for enrollment after these assessments will be discontinued.

Parents/guardians of study participants may request the results of their child's cognitive testing. In this case, the subject will receive a letter providing a basic interpretation of the results and referring the parent/guardian to the department's supervising neuropsychologist for any questions or concerns.

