#### Rationale

Emerging research suggests that inositol may have modest effects in the treatment of depression, but there have been no studies in children. Similar to the omega-3 fatty acids, inositol is well tolerated. Given that these nutritional supplements show promise in the treatment of mood disorders but to small effect, we propose to study the possible additive effect of combining these two alternative treatments in youth with bipolar spectrum disorders, an area of significant need.

We propose to conduct a randomized, double blind, controlled trial that will evaluate effectiveness and tolerability of omega-3 fatty acids and inositol used alone and in combination. We plan to decrease the variability in the population under study by limiting the age range to 5-12 years and excluding cases with significant, untreated, comorbidity. We will measure cognitive effects/side effects with a neuropsychological battery pre and post treatment. We will exclude subjects with a history of failing treatment with two or more conventional treatments.

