We will enroll 90 subjects to allow for randomization of 30 subjects into each treatment arm of the study. The subject's first visit to the office consists of a meeting with a study clinician who explains the study, obtains informed consent, and administers an abbreviated form of the structured diagnostic assessment (45-90 minutes). After the evaluation with the study clinician, the subjects will undergo a neuropsychological assessment (45-60 minutes).

We anticipate that subjects may enter this trial following completion of/withdrawal from other Bipolar Disorder protocols in our office, and that there may be procedural overlap. So as to not burden subjects/parents/guardians with redundant time commitments, we will use the following data if previously collected:

- **Diagnostic Data:** If a subject has completed an evaluation with one of the study clinicians and/or the structured assessment within the previous 12 months prior to entrance into this study, they will not be asked to repeat any overlapping diagnostic procedures. However, the study clinician will review the interval time period to assess for clinically significant medical or psychiatric history, to ensure that the subject meets appropriate study entrance criteria.
- **Cognitive and Neuropsychological Testing:** If the subset of scales assessing intelligence (WASI or KBIT-2 for 5 year-olds) and cognitive functioning (select WISC tasks or WPPSI-III tasks for 5 year-olds) in the neuropsychological battery

have been completed within 12 months prior to entrance into this study, subjects will not be asked to repeat these procedures at screening/baseline.

• Screening Rating Scales: If a parent has completed the Child Behavior Checklist (CBCL), Social Responsiveness Scale (SRS), or the Behavior Rating Inventory of Executive Function – Parent Form (BRIEF) within the past six months as part of one of our screening protocols, we will not ask the parent/guardian to repeat these scales at screening/baseline.

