# 8. Neuropsychological Tests/Cognitive Evaluation

IQ Testing: At study beginning, subjects will complete a brief cognitive screen. The scales we will use meet the demand for quick reliable measures of intelligence in clinical, educational and research settings. These tests will provide estimates of verbal and nonverbal ability respectively, as well as the direct measure of Full Scale IQ. This portion of the cognitive evaluation will take

approximately 30 minutes to complete. In the unlikely event that a subject's estimated IQ is below 70, the subject will not be eligible to participate in the study. Depending upon the subject's age, the cognitive screen will consist of:

- **Subjects age 5:** Verbal Knowledge, Riddles, and Matrices subtests of the Kaufman Brief Intelligence Test, Second Edition (KBIT-2)(Kaufman & Kaufman, 2004)
- Subjects ages 6-12: Vocabulary and Matrices subtests of the Wechsler Abbreviated Scale of Intelligence (WASI)(Wechsler, 2003)
- Cognitive Functioning Testing: At screening and endpoint, to assess the impact of treatment on cognition, we will assess basic intellectual and cognitive functions purported to be deficient in patients with bipolar disorder. Cognitive deficits that have been observed in bipolar disorder may reflect dysfunction in the frontal subcortical circuits that support aspects of attention, executive functions processing speed, memory and learning (Bearden, 2001). The neuropsychological battery we have developed to assess these functions includes both published clinical measures with large, normative samples and experimental measures with strong empirical evidence of validity. This neuropsychological battery, which has been used widely in clinical trials and family studies in our office, has been well tolerated. The testing will take approximately 25 minutes to complete. The ageappropriate testing will include:
  - Subjects age 5: Symbol Search and Coding subtests of the Wechsler Preschool and Primary Scale of Intelligence (WPPSI-III) (Wechsler & Sattler, 2002) to measure processing speed
  - Subjects ages 6-12: Digit Span and Coding subtests from the Wechsler Intelligence Scale for Children-Fourth Edition (WISC-IV) (Wechsler, 2003) to measure working memory and processing speed

The working memory scale will be omitted for subjects who are 5 years of age, as we do not have an age-appropriate scale available.

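### Pre-treatment cognitive and SAICA scores can be taken on a drug that is stopped before Baseline, so within-arm change in tapered children may mix drug withdrawal with supplement effect

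*Combined protocol and SAP*

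**What the plan says.** **What the scores are for.** The Rationale promises: "We will measure cognitive effects/side effects with a neuropsychological battery pre and post treatment". Section 8, under Neuropsychological Tests/Cognitive Evaluation, schedules the cognitive-function subtests "At screening and endpoint, to assess the impact of treatment on cognition". The SAICA entry in section 8 gives the same kind of purpose for social functioning.

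**When they are taken.** Section 7 (Design) describes the first office visit as consent, a diagnostic interview, and then testing: "After the evaluation with the study clinician, the subjects will undergo a neuropsychological assessment (45-60 minutes". Table 1 has the WISC-IV/WPPSI-III tasks and SAICA at visits 99 and 12 and nowhere else. "The above may take place over two visits over the course of three weeks, if necessary" is the only statement on spacing within screening.

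**Who is tapered, and when.** "Only subjects not responding to current treatment will be tapered from medication" (Washout Period). For drugs given for a comorbid condition, the decision starts at screening: "If at Screening a participant is taking medication for a comorbid condition, the clinician will evaluate, using a CGI scale for the targeted condition" (Concomitant Medications). A rating of moderate or worse leads to advice to taper. On duration: "Mood stabilizers/atypical antipsychotics are generally washed out over the course of 7 days, while stimulants are discontinued in 2 or 3 days"; antidepressants and atomoxetine typically take 7 days, with 14 for one antidepressant. The deadline for finishing is the Baseline Visit: "Any subjects requiring medication washout must be tapered off this medication prior to Baseline Visit as indicated in the washout section". From then on no drug may be added or changed, apart from limited lorazepam.

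**The concern.** A pre-post difference measures treatment only if the two tests differ in nothing else that matters. Here a child can be tested on a stimulant, antipsychotic, mood stabiliser or antidepressant, stop it, start the supplement, and be retested off the old drug. The protocol itself says that conventional drugs can affect cognition: Specific Aim III lists cognitive clouding among their side effects, and the Background mentions cognitive impairment. Stopping such a drug could look like a cognitive benefit of the supplement, or could hide a cognitive side effect of it.

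All three arms receive active treatment, so within an arm nothing allows the withdrawal component to be subtracted. At stake is how the within-arm cognitive and social-functioning changes are read.

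**Working it through.** The plan states no figure on this point, so there is none to reproduce. The check has three steps.

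**1. Visit order**

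| Measure | Pre-treatment value | Repeated at visit 0? |
|---|---|---|
| Cognitive-function subtests | Screening (section 8, Table 1) | No |
| SAICA | Screening (Screening Visit, Table 1); section 8 says only the beginning of the study | No |
| SRS, Impact on Family | Screening in their own section 8 entries and Table 1; baseline in the section 8 paragraph introducing the secondary measures | Documents disagree |
| YMRS, CDRS, HAM-D | Screening | Yes |
| GAF, CGI, Mania Checklist, ADHD Rating Scale, BPRS, PQ-LES-Q | Visit 0 | First taken there |

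Testing is described at the first office visit, tapers of comorbid-condition drugs are decided at or after the screening rating, and washout need only be finished by Baseline. Testing on the old drug is therefore permitted and is the likely order. It is not certain: washouts of 2–3, 7 or 14 days all fit within the three-week screening window, so a taper could come first.

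The re-use rule in section 7 adds a second route. It accepts cognitive scores up to 12 months old, and SRS forms up to six months old from a screening protocol, without reference to medication at the time.

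**2. Size within an arm**

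Let p be the share of an arm tapered after the pre-treatment test and w the shift in score (in SD units) from stopping the drug. The documents give neither, so both are assumptions. The shift is taken to have the same sign in every tapered child; opposite shifts for different drugs would partly cancel.

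Distortion of mean within-arm change = p × w:

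- p = 0.2, w = 0.3: 0.06 SD
- p = 0.5, w = 0.3: 0.15 SD
- p = 0.5, w = 0.5: 0.25 SD

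If the pre-treatment value is taken after washout, w = 0 and this component disappears.

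**3. Effect between randomised arms (30 per arm)**

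Taper status is settled before study treatment starts, so the expected difference in p between arms is zero. The chance difference has SD √(2p(1−p)/30). At p = 0.3 this is √(2 × 0.3 × 0.7/30) = 0.118, which is worth 0.118 × 0.3 = 0.035 to 0.118 × 0.5 = 0.059 score SD.

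For scale, assume a pre/post correlation of 0.7. The standard error of a between-arm difference in change is √(2 × (1 − 0.7)) × √(2/30) = 0.775 × 0.258 = 0.20 SD. Adding the larger chance component gives √(0.20² + 0.059²) = 0.21 SD.

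A two-arm ANCOVA simulation (30 per arm, same correlation, 3,000 runs per setting) agrees:

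| p | w | Within-arm shift, no true effect | Between-arm estimate, no true effect | Type I error | Power, true effect 0.5 SD |
|---|---|---|---|---|---|
| 0 | 0 | 0.001 | −0.001 | 0.053 | 0.757 |
| 0.25 | 0.3 | 0.077 | −0.001 | 0.053 | 0.749 |
| 0.5 | 0.3 | 0.150 | −0.001 | 0.049 | 0.743 |
| 0.5 | 0.5 | 0.252 | −0.004 | 0.049 | 0.719 |

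**The case against.** The strongest reply is that the one cognitive hypothesis in section 9 (Exploratory Hypothesis 1) compares the combination with each single treatment between randomised arms, and that section 9 specifies no within-arm cognitive test. This stands. A reader might infer that the between-arm comparison is biased, but randomisation balances tapering in expectation. Chance imbalance is ordinary sampling variation, and the loss of power is small.

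Three other inferences go further than the text:

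- *The pre-treatment scores always precede washout.* The Screening Visit section requires both testing and taper to be finished before Baseline but does not order them.
- *Every child is affected.* Partial responders and children on stable ADHD medication may keep their regimen, so their two tests are taken on the same drugs.
- *SRS and Impact on Family clearly share the problem.* One paragraph of section 8 already places both at baseline. For these two scales the firm finding is a contradiction to be reconciled.

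It is also fair to say that moving the test does not turn a within-arm change into a pure supplement effect, because retest practice and natural course remain. That limits the gain. It does not justify leaving in an avoidable confounder when the Rationale and section 8 read the pre-post change as a treatment effect.

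**Conclusion.** The point holds for within-arm change in tapered children, on the cognitive-function subtests and SAICA, and on SRS and Impact on Family if the screening timing applies. The distortion is about 0.06–0.25 SD if 20–50% of an arm is tapered and stopping the drug shifts scores by 0.3–0.5 SD in one direction. These inputs are assumptions; a smaller share or shift reduces the distortion in proportion. Exploratory Hypothesis 1 remains valid, with power falling from 0.757 to 0.719 in the most extreme setting simulated. The primary outcomes, YMRS and CDRS, are measured again at Baseline and are unaffected. The point concerns the interpretation of secondary and exploratory measures, and it is cheap to correct.

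**What to change.** - Keep the IQ screen at visit 99, where eligibility needs it.
- Take the cognitive-function subtests (about 25 minutes), SAICA, SRS and Impact on Family at visit 0, after any washout and before the first study dose, at least for every tapered child.
- State that the re-use rule in section 7 does not replace this measurement for a tapered child.
- Reconcile the timing in section 7 (first visit and re-use rule), the Screening Visit section, the section 8 entries for SAICA, Neuropsychological Tests, SRS and Impact on Family, the section 8 paragraph introducing the secondary measures, and Table 1.
- Record medication status at each test. Where only an on-drug score exists, keep the child in the analysis, in line with the intention-to-treat rule in section 9, and adjust or stratify for taper. Exclude such scores only in a sensitivity analysis.

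The cost is a protocol and Table 1 amendment and a longer baseline visit for these children. The tests and the visit already exist, so no new procedure is needed.
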